### **D. Specific methods and techniques used throughout the study**

#### **1. Intervention:**

*Virtual, group instruction:* Participants will be complete a total of 24, 1-hour group education sessions with a trained health educator. The group size will be 15-18 participants with continuous recruitment until reaching a total of 30 participants. Sessions will be delivered virtually (Zoom®). Prior to each group meeting, participants will be provided hard copy and audio/visual versions (podcasts and YouTube®) of the lesson to be covered in the upcoming meeting. group session will follow a pre-determined structure: group discussion, review of adherence, 5 to 10 minutes of physical activity, and an active learning-based education. Thus, active learning-based education will include: case vignettes, group debates/discussions, think-pair-share activities, gamification of health-related topics, creation of meal and physical activity, problem-solving barriers to a healthy diet and physical activity, and hands-on worksheets.

- i. Diet Prescription. Participants will receive a diet prescription of 1200-1500 kilocalories (kcals), consisting of 5 portion-controlled meals [(PCMs); 3 shakes and 2 entrees], 5 servings of fruits and vegetables, and zero-calorie beverages. All PCM shakes will be prescribed from the company Health Management Resources (HMR), consisting of 100 kcals and 10g of protein/shake. PCM entrees are available either via HMR or approved outside entrees for purchase at the grocery store as determined by the RD. Guidelines for the approved outside entrees are <300 kcals, <10g sugar, and <3g saturated fat per PCM. Participants will be encouraged to consume at least 65 ounces of zero-calorie beverages per day. Adherence to the diet prescription will be monitored via weekly self-monitoring sheets submitted to the RD by email prior to the educational session for review and feedback.
- ii. Exercise Prescription. Participants will be asked to engage in 45 minutes of moderate- to-vigorous exercise 5 days per week or 50,000 steps per week. A pedometer will be available for purchase if desired, but participants may use personal step counting devices (e.g.,

phone apps, watches). Adherence to the prescribed MVPA and steps will be assessed using weekly self-monitoring sheets submitted to the RD via email prior to each session.

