## 2. Schedule of Evaluations

	Screening Visit: (Day-30 to Day-1)	Baseline (Day-30 to Day-1):	Weekly	End of Study (Week 24)
Informed Consent	X			
Enrollment	X			
Anthropometrics	X		X	
Health History		X		X
Quality of Life		X		X
Self-Efficacy		X		X
Diet Behaviors		X		X
Session Attendance			X	
Diet Adherence			X	
Exercise Adherence			X	

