## 3. Description of Evaluations

a. Anthropometrics (Weight, Height, Waist Circumference): Participants will be weighed at the KU Weight Management Clinic location in Kirmayer Fitness Center on the main KU Medical Center campus. Anthropometrics will be collected in a private room by a registered nurse prior to the participant seeing a clinic physician. Weight will be collected to the nearest 0.1 kg. Standing height will be measured using a stadiometer. Body Mass Index will be calculated as weight (kg) divided by height (cm) squared. Waist circumference will be measured at the midline level between the inferior margin of the ribs and the superior border of the iliac crest.

b. Health History: A health history developed by the study team will be completed online via the REDCap database. Questions include a comprehensive assessment of previous weight loss attempts, current and previous medical conditions, current medications, and previous medical procedures.

c. Quality of Life: Quality of life will be assessed using the Short Form 36 Health Survey Questionnaire (SF-36). The SF-36 is a validated and commonly utilized survey ( $\alpha > 0.85$ ) that relies on self-report of 8 domains: limitations in physical activities because of health problems, limitations in social activities because of physical or emotional problems, limitations in usual role activities because of physical health problems, bodily pain, general mental health, limitations in usual role activities because of emotional problems, vitality, and general health perceptions (Brazier et al., 1992).

d. Self-Efficacy: Self-efficacy will be assessed using two tools: the Health Eating and Weight Self-Efficacy (HEWSE) scale and the Self-Efficacy for Exercise (SEE) scale. Both surveys will be completed at baseline and post-intervention via REDCap. The HEWSE is an 11-item scale to measure healthy eating and weight-selficacy with good internal consistency ( $\alpha > 0.80$ ) and test-re-test reliability ( $r = 0.72$ ) (Wilson-Barlow et al., 2014). The SEE is a 9-item scale that measures confidence engaging in exercise 3 times per week for 20 minutes ( $\alpha = 0.9$ ) (Resnick & Jenkins, 2000).

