**V. Data Analysis and Reporting**

**A. Statistical and Data Analysis**

The effectiveness of the intervention will be assessed by estimating a confidence interval for weight loss percent at 3 months. If the 95% CI includes 5% and the observed weight loss exceeds 2.5%, we will consider that the clinical effectiveness of the intervention is plausible and will seek to confirm this in a larger trial. We evaluated the operating characteristics of this decision rule through simulation with  $n = 36$  and assuming 15% attrition. When the true weight loss percentage is at least 5% we will have a 97.5% probability of proceeding, while if the true weight loss was not clinically significant, e.g., weight loss of 4% or 2.5% we would have a 57% and 1% chance of proceeding respectively. This will ensure that we do not proceed when the true effectiveness is much less than has been determined clinically relevant. We will compare our observed recruitment, attendance, and adherence to observed values from our traditional weight management program ( $88 \pm 5\%$  recruitment,  $75 \pm 8\%$  attendance,  $80 \pm 3\%$  adherence) and previous studies utilizing the same diet plan, we expect to see similar rates in this intervention and will evaluate any characteristics of this trial which led to lower than expected rates for potential modification for a follow-up trial. The recruitment goal is set at 30 participants to account for 10-15% attrition and statistical analysis of a sample size of at least 24 participants. All statistical analyses will be conducted using SAS software version 9.4 or higher with a significance level set at 0.05.

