**B. Outcome**

We expect to know the feasibility of the intervention and determine if we should apply for external funding to complete an adequately powered trial.

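### The 3-month proceed decision has no defined analysis set or missing-weight rule, and the rule as worded does not match its stated 97.5%

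*Combined protocol and SAP*

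**What the plan says.** The study is single-arm (II.B). V.A rests the effectiveness decision on a confidence interval for percent weight loss at 3 months. The rule reads "If the 95% CI includes 5% and the observed weight loss exceeds 2.5" (per cent), and meeting it leads to a larger trial. V.B confirms that the purpose is to "determine if we should apply for external funding to complete an adequately powered trial".

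The rule's performance was simulated with n = 36 and 15% attrition: "When the true weight loss percentage is at least 5% we will have a 97.5% probability of proceeding", with 57% at a true loss of 4% and 1% at 2.5%. On size, V.A says "The recruitment goal is set at 30 participants to account for 10-15% attrition" and to allow "statistical analysis of a sample size of at least 24 participants".

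No section names an analysis set, a rule for a missing 3-month weight, or a sensitivity analysis. The only data-handling rule is the outlier re-check in IV.C. II.H removes some participants from the intervention after a serious adverse event and does not mention later weights.

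On how weights are obtained, II.D.2 marks "Anthropometrics" at screening and weekly. II.D.3 says "Participants will be weighed at the KU Weight Management Clinic location", while II.D.1 says "Sessions will be delivered virtually".

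**The concern.** The plan expects attrition but treats it only as lost sample size. With one arm and a fixed 5% benchmark, no comparison group can offset selective dropout. If those without a 3-month weight have lost less than those with one, the mean of the observed weights is too high for the enrolled group. Leaving the set unstated also allows it to be chosen after the weights are seen.

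The direction of the effect depends on what the rule means. If it means that the upper 95% limit is at least 5%, overstated loss makes proceeding more likely. If it means literally that the interval contains 5%, overstated loss above 5% can block proceeding. The rule's wording therefore has to be settled at the same time.

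**Working it through.** **1. Sizing.** Enrolment needed for 24 analysed is 24/(1 − d):
- d = 10%: 26.7, so 27
- d = 15%: 28.2, so 29
- d = 20%: 30

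The stated 30 is reproduced to within one at 15%. Going from 30 enrolled to 24 or more analysed removes leavers from the count, hence the inference of completers. The floor of 24/30 would allow 20% missing.

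**2. The stated 97.5%, 57% and 1%.** The simulated sample after attrition is 36 × 0.85 = 30.6, about 31. The interval is mean ± t × s/√n. The plan gives no SD; solving for 57% at a true 4% gives about 3.0 (assumed from here on).

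| True loss | Stated | Upper limit at least 5% | Interval contains 5% |
|---|---|---|---|
| 5% | 97.5% | 97.5% | 95% |
| 4% | 57% | 57% | 57% |
| 2.5% | 1% | 0.6% | 0.6% |
| 6.5% | at least 97.5% implied | about 100% | 23% |

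Hand check of the last cell: the half-width is 2.042 × 3.0/√31 = 1.10, so the interval contains 5% only if the mean is at most 6.10. The probability is Φ((6.10 − 6.5)/0.539) = Φ(−0.74) = 0.23. The plan claims its 97.5% for any true loss of at least 5%, so only the upper-limit reading fits.

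All 36 analysed with an SD of about 3.27 fits the stated figures equally well. The simulation therefore does not reveal the analysis set or how dropout was generated.

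**3. Bias of a completer mean.** The enrolled mean is (1 − d)C + dL, where C is the completer mean and L the leaver mean. The overstatement is C minus this, which is d(C − L). With C = 4.5 and L from 2 to 0 (assumed):
- d = 10%: 0.25 to 0.45 points
- d = 15%: 0.38 to 0.68 points
- d = 20%: 0.50 to 0.90 points

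**4. Effect on the decision.** Simulated with N = 30, SD 3.0, each person missing with probability d, t-based interval, upper-limit reading and C = 4.5%:

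| Missing | Leavers | Completers proceed | All weights known |
|---|---|---|---|
| 5% | 0% | 86-87% | 78% |
| 10% | 0% | 87% | 67% |
| 15% | 0% | 88% | 56% |
| 15% | 2% | 88% | 69% |
| 15% | 4.5% | 88% | 86% |
| 20% | 0% | 88% | 44% |

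The row with leavers at 4.5% shows that the gap comes from selective dropout, not from the smaller number. At 15% missing with leavers at 0%, other SDs give 84% against 45% (SD 2.5) and 93% against 78% (SD 5.0).

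If the enrolled group truly loses 2.5% and leavers lose nothing, completers proceed about 4%, 9% and 17% of the time at 10%, 15% and 20% missing. With all weights known the figure is 1-2%.

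Under the literal reading the direction reverses. At 15% missing with leavers at 2%, completers at 6.5% proceed 32% of the time, against 74% with all weights known.

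**5. The planned size.** With N = 30, SD 3.0 and 15% dropout unrelated to loss, the upper-limit rule gives about 97.5%, 63% and 2% at true 5%, 4% and 2.5%. The stated 57% and 1% belong to n = 36.

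**The case against.** The best reply is that the size of the bias is assumed. The documents give no SD and nothing on how leavers fare. They do not say whether the 10-15% attrition is by 3 months or over 24 weeks, so fewer weights may be missing at the decision point. The 20% row goes beyond the stated attrition, since 24 is a floor. All of this stands: the figures are illustrations, and the effect is nil if leavers lose the same.

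The remedy has limits too. A repeated-measures model assumes missing at random. In simulation at 15% missing (completers 4.5%, leavers 0%, weights at weeks 4, 8 and 12), it cut the chance of proceeding from 88% to 62% when leavers had been slow throughout; the full-data figure was 55%. It removed almost nothing (87% to 86%) when leavers matched the others until leaving, and nothing when they had no weight after baseline. It also needs interim weights whose collection is unclear. This stands and shapes the fix.

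A reader might infer more than the documents support:
- **That the plan specifies a completer analysis.** It does not; the sizing only suggests one.
- **That 97.5%, 57% and 1% would describe this trial if dropout were unrelated to loss.** They were computed at n = 36, the dropout mechanism is not given, and at 30 the last two become about 63% and 2%.
- **That a false efficacy claim would follow.** The rule calls effectiveness only plausible and leads to a confirmatory trial.

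**Conclusion.** The point holds as an omission with a conditional consequence. No analysis set or missing-weight rule exists for the estimate that decides the next step, and the design cannot absorb selective dropout. Under the assumptions above (SD 3.0, 30 enrolled, completers at 4.5%, leavers at 0-2%, upper-limit reading), a completer analysis raises the chance of proceeding to about 88% from 56-69% at 15% missing. At 5% missing with leavers at 0%, the gap is about 9 points.

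The mismatch between the rule's wording and its stated 97.5% needs no assumption about leavers. A 95% interval contains a true value of 5% about 95% of the time, and contains 5% less often as true loss rises above it.

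The change is advisable rather than essential. The harm is a possibly wrong decision about seeking a larger trial.

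**What to change.** In V.A:

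1. Define the primary set as all enrolled participants with a baseline weight. Seek the 3-month weight from everyone, including those who stop attending.
2. Estimate mean 3-month percent change with a repeated-measures model using whatever interim weights exist. State that it assumes missing at random and does not correct for people with no weight after baseline. If few interim weights exist, report the observed-weight estimate, labelled as such.
3. Repeat the rule with missing 3-month weights set to 0% loss, and report the number missing. If the two results disagree, report the proceed conclusion as sensitive to dropout.
4. Word the rule as an upper 95% limit of at least 5% with observed loss above 2.5%, or else restate the 97.5%.
5. Re-run the operating characteristics at 30, stating the SD, the dropout mechanism and the analysis set. Do not simply add a note that the n = 36 figures assume unrelated dropout.
6. Reconcile II.D.1, II.D.2 and II.D.3 on how weekly weights are obtained.

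The cost is a few sentences, a standard SAS procedure, a short re-simulation, and the effort of contacting people who stop attending. The estimate may be slightly less favourable. The 0%-loss analysis is deliberately harsh: at 15% missing it proceeds only about 51% of the time even when leavers lose the same 4.5%. It therefore serves as a sensitivity analysis and not as the primary result.

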**B. Outcome**

We expect to know the feasibility of the intervention and determine if we should apply for external funding to complete an adequately powered trial.

### C. Study results to participants

Study results will not be sent to the participants.

### D. Publication Plan

The research results will be presented at a conference and published in a peer-reviewed journal upon completion of the pilot study.

